# CLINICAL TRIAL PROTOCOL

### Saroglitazar Magnesium SARO.20.001

# CONFIDENTIAL Page 34 of 109

- 11) Unstable pulmonary disease (based upon site investigator's evaluation) at screening.
- 12) Use of drugs that are known CYP2C8 inhibitors/substrates (Refer Appendix 2 for the 'List of Known CYP2C8 Inhibitors/Substrates') in the last 28 days prior to screening.
- 13) History of severe illness or any other conditions that require systematic treatment/or hospitalization, until participant either completes therapy or is clinically stable on therapy as per the opinion of the investigator, for at least 7 days prior to screening (such as poorly controlled psychiatric disease, active gastrointestinal conditions that might interfere with drug absorption, etc.).
- 14) Use of thiazolidinediones or Telmisartan within 3 months prior to screening or until time of randomization.
- 15) Use of unstable doses of SGLT2 inhibitors (e.g. canagliflozin, empagliflozin, dapagliflozin, etc.), glucose-dependent insulinotropic polypeptide (GIP) and/or GLP-1 agonists (e.g. semaglutide, exenatide, liraglutide, lixisenatide, tirzepatide etc.) within 6 months prior to screening until time of randomization.
- 16) Use of pentoxifylline, ursodeoxycholic acid, antioxidants such as vitamin E (>200 IU/day), glutathione, orlistat, betaine, or non-prescribed complementary alternative medications within 6 months prior to screening until time of randomization.
- 17) Known allergy, sensitivity or intolerance to the study medication or formulation ingredients.
- 18) History of any known bleeding disorder or coagulopathy.
- 19) Any condition that in the opinion of the site investigator, would compromise the participant's ability to participate in the study.
- 20) Unstable doses of anti-diabetic agents including sulfonylureas, biguanides or DPP-4 inhibitors in the last 3 months prior to screening until time of randomization.
- 21) Unstable doses of lipid lowering agents such as statins (e.g. simvastatin, pravastatin, atorvastatin, fluvastatin, lovastatin, rosuvastatin, etc.) or fibrates (clofibrate, Fenofibrate) in the last 3 months prior to screening until time of randomization.
- 22) Participant with weight change >5% within 6 months prior to screening until time of randomization.
- 23) History of bariatric surgery or currently undergoing evaluation for bariatric surgery.
- 24) Participation in another interventional clinical study and/or receipt of any other investigational medication within 3 months prior to screening.
- 25) History of COVID-19 infection in the last 30 days prior to screening.
- 26) Pregnancy-related exclusions, include:
  - a. Pregnant/lactating female (including positive pregnancy test at screening)
  - b. Pregnancy should be avoided by male and female participants either by complete abstinence or the use of acceptable effective contraceptive measures for the duration of the study and for at least 1 month after the end of the study treatment. Refer Appendix 3 Contraceptive Guidance
  - 27. Participants having an absolute contraindication to MRI (eg., any implants, magnetic metals, cardiac pacemakers, neurostimulator) as per investigators' discretion

Approved by: [name] No.: SARO.20.001
[name]	Version No.: 4.0

CONFIDENTIAL Page 35 of 109

#### 7.4 PARTICIPANT WITHDRAWAL

A participant may withdraw from the study at any time without penalty and for any reason without prejudice to her/his future medical care. Although a participant is not obliged to give his/her reason for withdrawing prematurely, the investigator will make a reasonable effort to obtain the reason while fully respecting the participant's rights. If there is a medical reason for withdrawal, the participant will remain under the supervision of the investigator for follow-up of AE(s) as detailed in Section 12.4.1.6.

Every effort will be made to continue clinical and/or laboratory follow-up, as appropriate, in participants who wish to withdraw from the study medication, and reasonable efforts will be made to contact a participant who fails to attend any follow-up appointments, in order to ensure that he/she is in satisfactory health. A participant's withdrawal of consent and agreement to undergo a final examination will be documented on the case report form (CRF) and on the investigator's copy of the informed consent form (ICF), which will be countersigned and dated by the participant. Safety follow-up within 4 weeks from the date of withdrawal will be conducted for all participants who receive the study medication but do not complete the study according to the study protocol.

#### 7.5 Screen Failure

A screen failure occurs when a participant who has signed the ICF does not meet all the entry criteria outlined in this protocol and has not been randomized.

Participants who fail to meet all the screening criteria will not be rescreened unless approved by the sponsor or its designee in writing. Screening laboratory tests may be repeated once following the approval of the sponsor or its designee, if the laboratory test results seem implausible or inaccurate. No study procedures (including safety follow-up) will be performed for these participants.

For participants who fail to meet the inclusion criteria or who meet at least one of the exclusion criteria, the investigator (or designee) will document on a screening form the reason for the screening failure.

# 7.6 DISCONTINUATION OF PARTICIPANTS FROM THE STUDY AND STUDY DRUG

#### 7.6.1 Discontinuation of Study Drug

#### 7.6.1.1. Discontinuation Due to AE/SAE

The following clinical events warrant discontinuation of the study drug; however, the participant will continue to be followed for safety, and the relevant laboratory tests will be performed until

Approved by: [name] No.: SARO.20.001
[name]	Version No.: 4.0

#### CONFIDENTIAL Page 36 of 109

the event has resolved, i.e., clinical laboratory value(s) has/have returned to baseline or is/are no longer of clinical significance.

- Any AE (CTCAE, Version 5.0 or higher) of Grade ≥3 that is possibly or likely study drugrelated
- Any AE of CTCAE Grade  $\geq$  4 regardless of attribution to the study drug.
- SAE that may be related to the study drug may warrant discontinuation, as per the discretion of the site investigator.
- In the opinion of the site investigator, continuation of the study drug poses a health risk to the participant

### 7.6.1.2 Drug Induced Liver Injury & Liver Function Monitoring

Monitoring of DILI will be done during this study as per Tables  $\underline{1}$  and  $\underline{2}$ :

A separate blinded HSAC will be established. The committee will review, monitor and adjudicate possible cases of DILI in the study (refer to Section 12.4.3).

(Note: Prior to using these tables, R ratio would be calculated as alanine aminotransferase (ALT)/ALT upper limit of normal (ULN) divided by alkaline phosphatase (ALP)/ALP ULN (ALT/ULN÷ALP/ULN).

Approved by: [name] No.: SARO.20.001
[name] Version No.: 4.0

CONFIDENTIAL Page 37 of 109

 $\begin{tabular}{ll} Table 1. Algorithm for Monitoring and Management of Elevated ALT in Participants with Normal or Elevated Baseline ALT^a \\ \end{tabular}$ 

Treatment emergent ALT elevations	Treatment emergent total bilirubin elevations	Liver-related Symptoms (as a variable)	Action b
Normal/near normal baseline a : ALT ≥5x ULN Elevated baseline a : ALT ≥3x baseline or ≥300 U/L (whichever occurs first)	Normal Participants with Gilbert's syndrome: No change in baseline TBL	None	Repeat ALT, AST, ALP, TBL, in 2-5 days. Follow-up for symptoms. Initiate evaluation for other etiologies of abnormal liver tests.
Normal/near normal baseline a : ALT ≥3x ULN Elevated baseline a : ALT ≥2x baseline or ≥300 U/L (whichever occurs first)	Normal Participants with Gilbert's syndrome: No change in baseline TBL	Severe fatigue, nausea, vomiting, right upper quadrant pain	Repeat ALT, AST, ALP, TBL, in 2-5 days. Follow-up for symptoms. Initiate evaluation for other etiologies of abnormal liver tests.
Normal/near normal baseline a ALT ≥8 x ULN Elevated baseline a : ALT ≥5x baseline or ≥500 U/L (whichever occurs first)	Normal Participants with Gilbert's syndrome: No change in baseline TBL	None	Interrupt study drug. Initiate close monitoring and workup for competing etiologies. Study drug can be restarted only if another etiology is identified and liver enzymes return to baseline.
Normal/near normal baseline a : ALT ≥3x ULN Elevated baseline a : ALT ≥2x baseline or ≥300 U/L (whichever occurs first)	TBL ≥2x ULN Participants with Gilbert's syndrome: Doubling of direct bilirubin or increased INR to >1.5	None	Interrupt study drug. Initiate close monitoring and workup for competing etiologies. Study drug can be restarted only if another etiology is identified and liver enzymes return to baseline.
Normal/near normal baseline a : ALT ≥5x ULN Elevated baseline a : ALT ≥3x baseline or ≥300 U/L (whichever occurs first)	Normal or elevated	Severe fatigue, nausea, vomiting, right upper quadrant pain	Interrupt study drug. Initiate close monitoring and workup for competing etiologies. Study drug can be restarted only if another etiology is identified and liver enzymes return to baseline.

ALP = alkaline phosphatase; ALT = alanine aminotransferase; AST = aspartate aminotransferase; INR = international normalized ratio; TBL = total bilirubin, ULN= upper limit of normal.

Modified from Chalasani N, Regev A. Drug-induced liver injury in participants with pre-existing chronic liver disease in drug development: how to identify and manage? Gastroenterology. 2016;151:1046-1051.

aElevated baseline is defined as ALT  $\geq$ 1.5x ULN. Normal/near normal baseline is defined as ALT < 1.5x ULN. In participants with a sizable stable decrease in ALT (>50% of the baseline value) during treatment, a new baseline, corresponding to the ALT nadir, should be established on an individual basis for subsequent determination of a DILI signal.

bThe actions of close observation, monitoring, and drug interruption often overlap. Occasionally, workup is initiated after drug interruption.

Approved by: [name] No.: SARO.20.001
[name]	Version No.: 4.0

CONFIDENTIAL Page 38 of 109

Table 2. Detection and monitoring of elevated serum alkaline phosphatase

Treatment Emergent Serum Alkaline Phosphatase (ALP) elevations	Serum Total Bilirubin	Action/Follow-up
>2 times upper limit of normal (ULN) or > 250 IU/L whichever comes first, (unless ALP not of hepatic origin)	Within normal range	
 
Work up for cholestasis
 
Repeat liver profile within one week
 
If there is progressive increase in ALP (e.g. increase by 50% from previous value) or there is associated doubling of direct bilirubin + exceeds ULN, interrupt the investigational product
 
Restart the investigational product only if a competing etiology is identified and ALP is returning close to baseline
 

>2 times ULN	≥ 2 times ULN or In case of pre-existing Gilbert's, doubling of direct bilirubin + exceeding ULN	
 
Work up for cholestasis
 
Interrupt the investigational product
 
Repeat liver profile within 2-3 days
 
Restart the investigational product only if a competing etiology is identified and ALP is returning close to baseline
 

1-2 times ULN	>3 mg/dl or In case of pre-existing Gilbert's, doubling of direct bilirubin + exceeding ULN	
 
Work up for cholestasis
 
Interrupt the investigational product
 
Repeat liver profile within 2-3 days
 
Restart the investigational product only if a competing etiology is identified and ALP is returning close to baseline
 

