- 8) Any of the following laboratory values at screening:
  - a. ALT or AST >250 U/L
  - b. Total bilirubin >1.5 mg/dL and direct bilirubin > 0.5 mg/dL (unless due to Gilbert's disease or atazanavir use per the opinion of the site investigator)
  - c. Platelet count <150,000/mm^3
  - d. Estimated glomerular filtration rate (e-GFR) <60 mL/min/1.73m^2 using the chronic kidney disease-epidemiology collaboration (CKD-EPI) equation (Refer Appendix 6 for 'CKD-EPI Calculator')
  - e. International normalized ratio (INR) >1.3.
  - f. Albumin < 3.6 g/dL
- 9) History of malignancy in the past 5 years and/or active neoplasm with the exception of superficial, non-melanoma, skin cancer.
- 10) Unstable cardiovascular disease, including:
  - a) Unstable angina, (i.e., new or worsening symptoms of coronary heart disease) and/or acute myocardial infarction within the 3 months preceding screening
  - b) Acute coronary syndrome or coronary artery intervention within the 3 months preceding screening,
  - c) Heart failure of New York Heart Association (NYHA) class (III-IV) or worsening congestive heart failure within the 6 months preceding screening.
  - d) History of (within 3 months preceding screening) or current unstable cardiac dysrhythmias.
  - e) Uncontrolled hypertension (systolic blood pressure [SBP] >155 mmHg and/or diastolic blood pressure [DBP] >95 mmHg) at screening.
  - f) Stroke or transient ischemic attack within the 6 months preceding screening.

Approved by: [name] No.: SARO.20.001
[name]	Version No.: 4.0

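### The DILI tables in Protocol Section 7.6.1.2 give no action to three raised-bilirubin combinations although a milder liver picture has one

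*Protocol*

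**What the plan says.** Section 7.6.1.2 directs that DILI monitoring follow Tables 1 and 2. Table 1 combines ALT, a bilirubin column headed "Treatment emergent total bilirubin elevations", and liver-related symptoms as a separate variable. Its ALT thresholds depend on baseline: "Normal/near normal baseline is defined as ALT < 1.5x ULN". For that near-normal group the rows are:

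- Row 1: ALT ≥5x ULN, normal TBL, no symptoms: repeat tests.
- Row 2: ALT ≥3x ULN, normal TBL, symptoms: repeat tests.
- Row 3: ALT ≥8x ULN, normal TBL, no symptoms: interrupt.
- Row 4: ALT ≥3x ULN, "TBL ≥2x ULN Participants with Gilbert's syndrome: Doubling of direct bilirubin or increased INR to >1.5", no symptoms: interrupt.
- Row 5: ALT ≥5x ULN, TBL "Normal or elevated", symptoms: interrupt.

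Rows 1 to 3 add a line for one group only: "Participants with Gilbert's syndrome: No change in baseline TBL". Footnote b says "The actions of close observation, monitoring, and drug interruption often overlap".

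Table 2 has three rows:

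- Row 1: ALP >2x ULN or >250 IU/L with normal TBL: work-up and repeat tests, with interruption if ALP keeps climbing or direct bilirubin doubles and exceeds ULN.
- Row 2: ALP >2x ULN with TBL ≥2x ULN: interrupt.
- Row 3: ALP 1-2x ULN with TBL >3 mg/dL: interrupt.

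Rows 2 and 3 also carry a direct-bilirubin alternative for Gilbert's.

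**The concern.** Interruption rules should not give less action as the liver picture gets worse. Here the bilirubin entries jump from normal to ≥2x ULN, and the row that acts on ALT ≥3x ULN with TBL ≥2x ULN is closed to participants with symptoms. A site that applies the tables literally could interrupt drug at normal bilirubin and at TBL ≥2x ULN but find no instruction in between. It could also find that an interruption lapses when symptoms appear. DILI is an adverse event of special interest (Section 11.9.4), and these tables are the stated rule for it. The gaps arise for a participant whose TBL is normal at baseline and rises on treatment, so they do not depend on how a raised baseline is read.

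**Working it through.** No plan figure needs reproducing; the check is a row-by-row match. All inputs are the row conditions in Section 7.6.1.2, for participants without Gilbert's.

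**Table 1, near-normal baseline ALT.** Three ALT bands (3 to <5x, 5 to <8x, ≥8x ULN) × three TBL bands (normal, 1-2x, ≥2x ULN) × symptoms no/yes = 18 cells. One test value per band, with the rows met:

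| Symptoms | TBL (x ULN) | ALT 4.0x | ALT 5.5x | ALT 8.25x |
|---|---|---|---|---|
| No | 0.9 | no row | 1 (repeat) | 1+3 (interrupt) |
| No | 1.6 | no row | **no row** | **no row** |
| No | 2.67 | 4 (interrupt) | 4 (interrupt) | 4 (interrupt) |
| Yes | 0.9 | 2 (repeat) | 2+5 (interrupt) | 2+5 (interrupt) |
| Yes | 1.6 | **no row** | 5 (interrupt) | 5 (interrupt) |
| Yes | 2.67 | **no row** | 5 (interrupt) | 5 (interrupt) |

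Six cells have no row. The four in bold are anomalies, because a cell no worse on ALT, TBL or symptoms has an action. The other two (ALT 3 to <5x, no symptoms, TBL below 2x ULN) are not, because no milder cell has an action.

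**Crossing with Table 2.** The TBL ULN is not in the documents; take 1.0 to 1.3 mg/dL.

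- TBL 1-2x ULN: the upper end of the band is 2 × 1.0 = 2.0 to 2 × 1.3 = 2.6 mg/dL, below row 3's 3 mg/dL. Row 1 needs normal TBL and row 2 needs ≥2x ULN. Table 2 therefore fills none of the bold cells at TBL 1.6x.
- Symptoms, ALT 4x, TBL 2.67x: at ULN 1.2 this is 3.2 mg/dL (3.2/1.2 = 2.67). Table 2 row 2 interrupts if ALP is >2x ULN, and row 3 interrupts if ALP is 1-2x ULN. If ALP is not raised, neither table has a row, whereas the same values without symptoms are interrupted under Table 1 row 4.

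**Table 2 alone.** ALP 2.5x ULN at TBL 0.9x / 1.6x / ≥2x ULN meets row 1 / no row / row 2. The result is the same at a TBL ULN of 1.0, 1.2 or 1.3 mg/dL.

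**Elevated baseline ALT, B (U/L).** Rows 2 and 4 start at min(2B, 300), rows 1 and 5 at min(3B, 300), and row 3 at min(5B, 500).

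- Symptomatic gap at raised TBL, from min(2B, 300) to below min(3B, 300): B = 80 gives 160 to <240; B = 120 gives 240 to <300; B = 150 gives 300 to <300, which is empty. It stays empty for any higher B.
- No symptoms, TBL 1-2x ULN: the gap starts at min(3B, 300) and remains at every B. At B = 80, normal TBL gives repeat tests from 240 U/L and interruption from 400 U/L; TBL 1-2x ULN gives nothing.
- B = 80 counts as elevated if the ALT ULN is at most 80/1.5 = 53.3 U/L (an assumption).

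**The case against.** The best defence is that the rows are minimum severities. On that reading all three gaps close, and the remaining empty cell (no symptoms, ALT 3 to <5x, TBL 1-2x ULN) is not claimed here. The table is also not a strict partition: rows 1 and 3 overlap, as do rows 2 and 5. But nothing in the section says that a row extends to worse bilirubin or to added symptoms. Row 5 spells out that any bilirubin qualifies, so the authors wrote this where they meant it. Rows with and without symptoms also carry different ALT thresholds. Footnote b concerns actions that overlap and assigns none to a combination that meets no row. If minimum severity was intended, the fix only writes it down.

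Backstops exist: the discontinuation criteria and investigator opinion in 7.6.1.1, repeat testing as indicated in 9.4, follow-up of adverse events in 12.4.1.6, and the adjudication committee in 12.4.3. They reduce the risk. They rest on grading, attribution or judgement, and do not supply the missing row.

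Three stronger readings are tempting and not supported:

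- A reader might infer that TBL 1-2x ULN without symptoms is an error at any ALT. At ALT 3 to <5x ULN there is no row at normal TBL either, so this is the plan's own choice.
- A reader might infer that symptoms always remove the interruption at ALT 3 to <5x with TBL ≥2x ULN. Table 2 has no symptom column and still interrupts some of these cases when ALP is raised.
- A reader might infer that stable raised bilirubin is mishandled, since criterion 8b excludes "Total bilirubin >1.5 mg/dL and direct bilirubin > 0.5 mg/dL (unless due to Gilbert's disease or atazanavir use" and so admits some raised baselines. Table 1's column counts only treatment-emergent rises. Table 2's column lacks that qualifier, so an unchanged value above 3 mg/dL with a new ALP of 1-2x ULN literally triggers interruption. That errs on the cautious side and has a restart route. It is a minor matter outside this point.

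**Conclusion.** The tables are wrong as written. For participants without Gilbert's and with near-normal baseline ALT, three combinations have no action although a milder one does:

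1. No symptoms, ALT ≥5x ULN, TBL above 1x but below 2x ULN. At ALT ≥8x ULN the drug is interrupted on either side of this band but not within it.
2. Symptoms, ALT 3 to <5x ULN, any raised TBL, where Table 2 does not itself interrupt, for example when ALP is not raised. At TBL ≥2x ULN this is the most serious gap.
3. ALP >2x ULN with TBL between 1x and 2x ULN.

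Elevated baseline ALT shows the same pattern at its own thresholds, and the symptomatic gap disappears at baseline ALT ≥150 U/L. The conclusion rests on reading the bilirubin and symptom entries literally. The ULN values are assumptions and affect only the crossing with Table 2 and whether a given baseline ALT counts as elevated.

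How often these combinations would occur cannot be estimated from the documents. The SAP introduction records termination with four participants randomised, so at most four could be affected. Nothing here implies bias between arms, since the same rules apply to both under blinding.

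**What to change.** - Table 1 row 4: change the symptom entry from *None* to with or without symptoms.
- Table 1 rows 1 to 3: replace *Normal* and the Gilbert's line with: row 4 bilirubin condition not met.
- Table 2 row 1: replace the normal-range entry with: row 2 bilirubin condition not met. Keep its direct-bilirubin interruption rule.
- Keep the absolute TBL limits and the Gilbert's-only alternatives.

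On the 18-cell grid this leaves two cells without a row (ALT 3 to <5x, no symptoms, TBL below 2x ULN) and no anomalies. ALP 2.5x ULN with TBL 1.6x ULN then meets Table 2 row 1.

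Direct-bilirubin doubling should not replace the TBL limit for raised baselines other than Gilbert's, because that would drop a current interruption. Example at an assumed ULN of 1.2 mg/dL, without symptoms: TBL rises from 1.3 to 3.2 mg/dL, direct bilirubin from 0.4 to 0.7, ALT is 4x ULN and INR is normal. Row 4 interrupts now (3.2/1.2 = 2.67x ULN). Under a doubling rule it would not, because 0.7/0.4 = 1.75.

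The cost is a few reworded cells, and a few more repeat tests or temporary interruptions at TBL 1-2x ULN. In this trial, what remains is to check the four participants' laboratory listings (SAP 13.2) against the missing combinations and to correct the tables before they are reused.

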#### 7.6.1.3 Temporarily interrupting the study drug for important biological considerations:

- Total CPK >5x ULN (if normal at baseline), or >5x baseline (if elevated at baseline)
- Total CPK >3 x ULN (if normal at baseline) or >3x baseline (if elevated at baseline) associated with:
  - a. Elevation for more than 2 weeks OR
  - b. Symptoms concerning for rhabdomyolysis/myositis.
- Estimated glomerular filtration rate (e-GFR; calculated from CKD-EPI Equation) ≤40 mL/min/1.73 m² and where the value is reconfirmed between 24 to 72 hours from the time the site is made aware of the initial results Additionally, any participant who requires renal replacement therapy for any reason should also be discontinued from the study medication.
- Complete blood counts (CBCs): hemoglobin <10 g/dL; platelets <100,000/μL; and absolute neutrophil count <1,000 /μL.

#### 7.6.2 Discontinuation of Participant From the Study

A study completion CRF, which includes the reason for discontinuation, must be completed for all participant who are discontinued from the study. If the participant is discontinued

Approved by: [name] No.: SARO.20.001
[name]	Version No.: 4.0

#### CONFIDENTIAL Page 39 of 109

prematurely, the study completion CRF should clearly indicate the reason for discontinuation. If the participant discontinues due to an AE, an AE CRF must be completed.

- 1. Participant's decision to withdraw consent for trial participation: In case of withdrawal of consent and unless otherwise stated by the participant in the withdrawal of consent, investigator will be encouraged to obtain information from the participant in order to follow the medical status of the participants (especially when the participant withdraws his/her consent after having experienced an AE/SAE or an efficacy endpoint). Principal Investigator or designee(s) must make reasonable attempts to contact participants that are lost to follow-up, in order to obtain health status and reason for withdrawal. These attempts must be documented in the study forms.
- 2. Noncompliance to the protocol requirements, including any major deviation which may influence the results/outcome of primary endpoint or participant safety.
- 3. Either the investigator or the sponsor decides that discontinuing the participant from the study is in the participant's best interest.
- 4. A participant may also be discontinued from the study by the regulatory authorities or institutional review board (IRB).
- 5. If the participant becomes pregnant, as specified in Section 12.4.5.

